#### **6.6.3 Comparison of Investigator and Subject Assessment of AV Severity**

The IGA and Subject perception of AV severity at Week 12 will be compared and reported using descriptive statistics, to portray the level of concordance/discordance in stakeholder perceptions. This analysis will be conducted for the entire cohort and for select subgroups outlined in Section 6.3.2. Correspondingly, the Investigator and Subject responses to the questions related to AV severity at baseline will also be compared and reported using descriptive statistics.

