## PROTOCOL SUMMARY

Title:	Patient-reported Outcomes for Sarecycline Effectiveness and Safety (PROSES).
Précis:	A prospective cohort study of patients with acne vulgaris (AV) treated with sarecycline and followed for 12 weeks post treatment-initiation. Patient Reported Outcomes (PROs) and clinical profile of patients will be gathered for descriptive analyses of patient outcomes over the 12 week study observation period.
Objectives:	Evaluate PROs and clinician reported outcomes among patients with moderate to severe non-nodular AV who are prescribed sarecycline in clinical practice settings in the U.S.  Primary : Evaluate PROs related to Acne symptoms and impact.  Secondary : Evaluate sarecycline treatment effectiveness, in terms of IGA of AV severity on the face.  Additional : Evaluate clinician satisfaction with sarecycline treatment, sarecycline safety/tolerability, and concordance in perception of facial AV severity among clinicians and patients.
Population:	Three hundred (300) patients of age $\geq 9$ years at the time of initiation of treatment with sarecycline from clinical practices across the U.S. For pediatric patients, their parents/primary caregivers will also be recruited.
Number of Sites:	Maximum of fifty sites will be recruited.
Duration of Treatment	12 weeks.
Study Drug & Mode of Administration	Seysara® tablets; 60 mg, 100 mg, 150 mg, providing a dose of approx. 1.5mg/kg/day; oral. Commercial supply of medication may be supplied to clinical sites/Subjects for the duration of the study.
Study Duration:	Approximately eighteen months of study duration, including study set-up, 12 weeks of subject observation period and study close out followed by study data analyses.

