## 2.2 Study End Points

The primary endpoint of the study will be the PROs, in terms of self-perceived acne symptoms and impact of acne on emotional functioning, social functioning and activities of daily living, at Week 12.

The secondary endpoint will be the proportion of Subjects with Facial IGA success at Week 12, defined as a 2-point decrease in IGA score from baseline and a score of 0 (clear) or 1 (almost clear).

Additional endpoints of the study will include:

- Proportion of Subjects for whom Site Investigator reported 'very satisfied' or 'satisfied' in the question on global satisfaction with sarecycline treatment, at Week 12.
- Description of changes in PROs from baseline, at Week 12.
- Frequency of documented adverse events (AEs) and severe adverse events (SAEs) during the 12-week study observation period.
- Comparison of Subject perception and Site Investigator perception of AV severity, at Week 12.

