#### **6.6.5 Comparison of Parent/Caregiver and Patient Perceptions of AV Severity and Impact**

Parent/caregiver and pediatric patient responses to the questions related to AV severity at Baseline and Week 12 will be compared and reported using descriptive statistics, to portray the

level of concordance/discordance in stakeholder perceptions, within the Subject age group of 12-17 yrs. This analysis will be conducted using FAS.

Responses to select EPQ items at Baseline and Week 12 related to worries about Acne and impact of acne on child's ability to reach future goals will be compared to corresponding questions to parents/caregivers to portray the level of concordance/discordance in stakeholder perceptions, within the Subject age group of 12-17 yrs. This analysis will be conducted using FAS.

Parent/caregiver and pediatric patient responses to the questions at Week 12 related to the parents' understanding of child's concerns will be compared and reported using descriptive statistics, to portray the level of concordance/discordance in stakeholder perceptions, within the Subject age group of 12-17 yrs. This analysis will be conducted for the entire relevant cohort using FAS.

No missing data imputation will be undertaken for these items.

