## 7 DATA TABLES

All patients who received at least one dose of sarecycline during the study observation period and had at least some data pertaining to ASIS and EPQ items (related to primary research objective) at Week 12 will be included in **Full Analysis Set (FAS)** to facilitate the planned descriptive analysis. Correspondingly, patients who completed the study survey at Week 12 will be included in FAS, since patients answering Week 12 survey will have completed all relevant PRO related questions.

Safety data analyses will be conducted among the Safety Population, that correspond to the entire study cohort that took at least one does of sarecycline. Correspondingly, all patients completing the baseline survey and took at least one dose of sarecycline, amounting to N=300 will be included in this analysis.

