### 7.3 Tables for comparison of patient and clinician data

For tables comparing patient and clinician data, the FAS dataset is used for analysis only in the instances patient data has corresponding clinician week 12 data. All data tables in this section pertain to FAS population.

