**Table 7.3.1. Acne Severity Evaluation for All Patients**

Question	Baseline (N=x)		Week 4 (N=x)		Week 8 (N=x)		Week 12 (N=x)	
	A9 Patient	S9A Clinician	A9 Patient	P2 Clinician	A9 Patient	P2 Clinician	A9 Patient	P2 Clinician
Overall, how is the patient's facial acne right now?	N, Mean (SD), Median, Min, Max							
Clear (0)	n (%)							
Almost Clear (1)	n (%)							
Mild (2)	n (%)							
Moderate (3)	n (%)							
Severe (4)	n (%)							
Clear/Almost Clear	n (%)							

NOTE: All patient data corresponds to data from adult patients, pediatric patients aged 12-17, and caregivers of patients aged 9-11.

Data from Clinician and Patient DCF used; X patients had missing data; The denominator for the percentages is the number of patients with available data (N=X).

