**Table 7.3.2. Acne Severity Evaluation for Adult Patients**

Question	Baseline (N=xx)		Week 4 (N=xx)		Week 8 (N=xx)		Week 12 (N=xx)	
	A9 Patient	S9A Clinician	A9 Patient	P2 Clinician	A9 Patient	P2 Clinician	A9 Patient	P2 Clinician
Overall, how is the patient's facial acne right now?	N, Mean (SD), Median, Min, Max							
Clear (0)	n (%)							
Almost Clear (1)	n (%)							
Mild (2)	n (%)							
Moderate (3)	n (%)							
Severe (4)	n (%)							
Clear/Almost Clear	n (%)							

Note: All patient data corresponds to data from adult patients,

Data from Clinician and Patient DCF used; X patients had missing data; The denominator for the percentages is the number of patients with available data (N=X).

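### The SAP aims to portray concordance between raters, but Tables 7.3.1 to 7.3.7 specify only each rater's own distribution, not how often two raters agree about the same patient

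*SAP*

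**What the plan says.** **Aim.** The SAP's Protocol Summary lists "concordance in perception of facial AV severity among clinicians and patients" among the additional objectives. SAP 6.6.3 says that the IGA and the subject's severity rating at Week 12 "will be compared and reported using descriptive statistics, to portray the level of concordance/discordance in stakeholder perceptions", with a similar comparison at baseline. SAP 6.6.5 makes three child-parent comparisons, each to portray the "level of concordance/discordance in stakeholder perceptions, within the Subject age group of 12-17 yrs". The endpoint list in SAP 2.2 is more modest: "Comparison of Subject perception and Site Investigator perception of AV severity, at Week 12".

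**Sample.** In SAP 7.3, "the FAS dataset is used for analysis only in the instances patient data has corresponding clinician week 12 data". SAP 7 adds that "patients who completed the study survey at Week 12 will be included in FAS".

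**Specified output.** Tables 7.3.1 to 7.3.4 place patient and clinician columns side by side at each visit; Table 7.3.4 (ages 12 to 17) adds a caregiver column. Tables 7.3.5 to 7.3.7 place parent beside child at baseline and Week 12. Figures 8.9 and 8.10 are captioned as drawn from these tables. Table 7.3.1 pools respondent types: "All patient data corresponds to data from adult patients, pediatric patients aged 12-17, and caregivers of patients aged 9-11". Tables 7.3.2 to 7.3.4 already separate them.

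**Imputation.** The interim list in SAP 6.3.1 includes the patient-clinician severity comparison with LOCF, using the same methods as the final FAS analyses. SAP 6.9 applies LOCF to the IGA and ASIS item 9. The SAP 7.3 shells do not mention LOCF.

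**The concern.** Concordance is a property of pairs: for this patient, did the two raters choose the same category? Two separate distributions answer another question, namely whether one group of raters scores higher overall. The columns can look almost identical while many individual pairs disagree, because disagreements in opposite directions cancel.

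With the specified output, a reader could learn whether patients as a group see their acne as worse than clinicians do. The reader could not learn how often a patient and the treating clinician, or a child and parent, agree about the same face. That is what SAP 6.6.3 and 6.6.5 set out to portray. If the paired summary is left unspecified, whether and how to produce it can be decided after the data have been seen.

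**Working it through.** The documents give no figure for agreement, so there is none to reproduce.

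**1. Read the shells for any paired cell.** Every cell in Tables 7.3.1 to 7.3.7 is one rater's own N, mean (SD), median, minimum and maximum (or range), or count and percentage by category or grouped category. No cell crosses two raters. Percent agreement, within-pair difference and kappa do not appear in the shells or in SAP 6.3.1, 6.6.3 or 6.6.5.

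**2. What two columns can prove.** Assume these Week 12 distributions over scores 0 to 4 (not trial data):

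- patient p = 10/40/28/17/5%, mean 0.40 + 0.56 + 0.51 + 0.20 = 1.67
- clinician q = 15/45/25/12/3%, mean 0.45 + 0.50 + 0.36 + 0.12 = 1.43

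Maximum exact agreement = Σ min(p, q) = 0.10 + 0.40 + 0.25 + 0.12 + 0.03 = 0.90, so at least 10% of pairs must disagree. Minimum exact agreement = Σ max(0, p + q − 1) = 0. From the margins alone, agreement lies anywhere between 0% and 90%.

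**3. A more realistic range.** Keep those margins and give the two ratings an underlying bivariate normal correlation (assumed). The printed columns are the same in every row:

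| Latent correlation | Exact agreement | Within one category | Patient worse | Clinician worse |
|---|---|---|---|---|
| 0.3 | 33.7% | 78.4% | 40.5% | 25.8% |
| 0.5 | 38.8% | 84.6% | 38.9% | 22.4% |
| 0.7 | 46.7% | 91.7% | 36.1% | 17.1% |
| 0.9 | 62.2% | 98.6% | 30.3% | 7.5% |

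**4. Sensitivity to the margins**, correlation 0.3 to 0.9:

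- Both raters at the clinician margins (no shift): exact agreement 35.5% to 67.7%.
- Patient at 5/25/35/25/10%, mean 2.10, a shift of 2.10 − 1.43 = 0.67 points: exact agreement 27.7% to 37.6%.

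The gap matters most when the two columns look alike; a large shift leaves less doubt.

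**5. Would a paired estimate be precise enough to use?** Assume 250 pairs. The 95% half-width is 1.96 × √[a(1 − a)/250]. At a = 0.337 it is 0.059, giving 27.8% to 39.6%. At a = 0.622 it is 0.060, giving 56.2% to 68.2%. For clustering, take the cap of ten subjects per site (Protocol 6.3.2) and an assumed intraclass correlation of 0.10. The design effect is 1 + 9 × 0.10 = 1.90, so half-widths grow by √1.90 = 1.38, to about 8 points. The two ends of the range remain well apart.

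**The case against.** The strongest reply is that the plan delivers what it lists. The SAP 2.2 endpoint is a comparison, and side-by-side distributions on a shared 0 to 4 scale are one. They show the direction and size of any group difference, and the sample is matched at Week 12 for patient and clinician. The analysis is exploratory, and the wording of SAP 6.6.3 would permit a cross-tabulation. All of this stands. It limits the importance of the point but does not remove it: SAP 6.6.3, SAP 6.6.5 and the summary name concordance as the aim, and the detailed shells contain nothing that measures it. The optional Pearson correlation in Protocol 12.3.3 does not help. It is not assigned to rater comparisons, is not carried into the SAP, and correlation is not agreement.

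Several stronger readings are not supported:

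- *The SAP rules out an agreement analysis.* It does not; it leaves one unspecified.
- *Differences between child and parent columns may only reflect missing answers.* Nothing suggests substantial missingness. SAP 7 expects everyone who answers the Week 12 survey to have completed the relevant questions.
- *The study is too small to distinguish moderate levels of agreement.* With 250 independent pairs, even 33.7% and 46.7% have separate intervals (27.8% to 39.6%, and 40.5% to 52.9%). These overlap only once clustering is allowed for.

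The figure images were not available for this review; the statement about Figures 8.9 and 8.10 rests on their captions.

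**Conclusion.** The point holds as a mismatch between stated aim and specified output. The shells identify group-level differences and, for matched columns, a minimum discordance. They do not identify agreement within pairs. Under the main assumed margins one table is compatible with exact agreement of about 34% to 62%; the range is wider with no shift between raters and narrower with a large one. The margins and latent correlations are illustrative assumptions, not trial data. That margins do not determine agreement does not depend on them.

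This is a cheap and worthwhile improvement, not a serious flaw. It affects one additional descriptive objective and its child-parent counterpart. No primary, secondary or safety result changes.

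**What to change.** Keep the marginal tables and add the following.

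1. **Severity item, Week 12.** Add a 5×5 patient-by-clinician cross-tabulation to each of Tables 7.3.2 to 7.3.4, so that caregiver proxies for ages 9 to 11 stay apart from self-ratings. Add a child-by-parent cross-tabulation to Table 7.3.4. Report percent exact agreement, percent within one category, and the share in which each rater scores worse.
2. **Observed pairs.** Use ratings actually made at Week 12, and state that this departs from the LOCF version in SAP 6.3.1 and 6.9. Carrying forward may set an old rating against a current one. The LOCF version can be shown beside it.
3. **Baseline, patient-clinician.** Give the cross-tabulation and percent exact agreement only, because eligibility limits the IGA to 3 or 4.
4. **Tables 7.3.5 to 7.3.7.** Add a cross-tabulation of child-parent pairs aged 12 to 17, the age group in SAP 6.6.5. Note that the paired questions differ: for example, the parent is asked about being concerned and the child about being worried, and the parent's own understanding is set against the child's view of it.
5. **Optional.** Confidence intervals that allow for clustering by site or clinician, and a weighted kappa. Kappa depends on the margins and should be read beside the cross-tabulation.

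The cost is a few shells and some programming on data already collected. Age-group figures will be imprecise: with an assumed 80 to 120 pairs, the half-width for exact agreement is about 9 to 11 points before any allowance for clustering. If few patients are aged 9 to 11, that group may support counts only.

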#### **6.6.4 CFB in PROs**

CFB in ASIS domain scores and subscale scores at Week 12 will be assessed (estimated as Week 12 score minus Baseline score). CFB will be first analyzed descriptively for the entire FAS cohort. For this analysis of domain scores, measures will be considered as continuous variables. No missing data imputation will be used. CFB in proportion of individuals reporting specific response for individual items of ASIS will be conducted by treating these variables as discrete variables, and grouping into top-2 or bottom-2 response scales (within the likert scale), as outlined in Section 6.3.1. Scoring, scaling, and the handling of missing data will be handled in accordance with the recommendations accompanying the ASIS documentation.

CFB in proportion of individuals reporting specific response for select individual items of ASIS, most specifically, items # 9 & 10, will be conducted by treating these variables as discrete variables, and grouping into top-2 or bottom-2 response scales (within the likert scale), as outlined in Section 6.3.1. CFB at Weeks 4 & 8 will be assessed in addition to Week 12. LOCF data imputation method will be used to impute responses to ASIS items # 9 & 10 for respective encounters for the Subjects with missing data at those encounters, prior to analyses. CFB for these two measures (with and without LOCF imputation) will be first analyzed descriptively for the entire cohort, and then analyzed for select subgroups (as outlined in Section 6.3.2) with measures that use LOCF imputation.

Items from EPQ will be analyzed individually and CFB in individual questions/items will be reported descriptively for relevant categories of responses (depending on the response scales). No missing data imputation will be undertaken for these items.

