#### **12.6.4 CFB in PROs**

CFB in ASIS domain scores and subscale scores at Week 12 will be assessed. CFB will be first analyzed descriptively for the entire cohort and select subgroups. Analyses will be provided for FAS. For this analysis, the domain scores will be considered as continuous variables. No missing data imputation will be used. Scoring, scaling, and the handling of missing data will be handled in accordance with the recommendations accompanying the ASIS documentation and will be described in more detail in the SAP.

CFB in select individual items of ASIS, most specifically, items # 9 & 10, will be conducted by treating these variables as continuous variables. Based on data availability, CFB at Weeks 4 & 8 will be assessed in addition to Week 12. CFB will be first analyzed descriptively for the entire cohort and select subgroups. LOCF data imputation method will be used to impute responses to ASIS items # 9 & 10 for respective encounters for the Subjects with missing data at those encounters, prior to analyses.

Items from Expert Panel Questionnaire will be analyzed individually and CFB in individual questions/items will be reported for relevant categories of responses (depending on the response scales) descriptively. More detailed portrayal of this planned analysis will be outlined in the study SAP. No missing data imputation will be undertaken for these items.

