## 6.3 General Statistical Procedures

### 6.3.1 Overview

Data from Site Investigators and study Subjects will be treated separately, and combined into one dataset, based on the study assessments of interest. Validated instruments will be scored according to developer guidelines, reporting domain scores and overall summary scores, as appropriate. Home-grown questions/items will be analyzed and reported individually, based on the respective response scales. Change from Baseline (CFB) in scores (for continuous variables) or proportions (for discrete variables) will be computed as Week-12 minus Baseline measure for respective question responses.

Discrete measures will be assessed using summary statistics encompassing percentage of Subjects reporting particular outcome measures. The statistical differences in discrete variables to compare different patient groups (for subgroup analysis) for a given measure at a particular timepoint (such as Baseline or Week-12), or CFB in proportion of patients reporting a particular response to an outcome measure at a particular timepoint (such as Week-12) will be assessed using a  $\chi^2$  test. In case of likert scales, to compute P-values for CFB in proportions, the top-two response categories (of a likert scale) for a given question at Baseline will be grouped together into a single group proportion (versus the rest of the population/responders all together) and compared to the same group proportion at Week-12; the procedure will be repeated for the bottom-two response categories (of a likert scale) for a given question, by grouping them together into a single group proportion and compare it to the same group proportion at Week-12. For example, for ASIS item # 1 (how oily is your face right now), proportion of patients reporting “Not at all/A little” at Baseline will be grouped together (vs. rest of the population/responders) and compared to proportion of patients reporting “Not at all/A little” at Week-12; similarly, proportion of patients reporting “Quite a bit/Very” at Baseline will be grouped together and compared to proportion of

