**Table 7.1.13. CFB in Patient Acne Severity and How Face Looks (without imputation)**

Domain	CFB in Proportion at Week 4 N=xx	p- value	CFB in Proportion at Week 8 N=xx	p- value	CFB in Proportion at Week 12 N=xx	p- value
Acne Severity (ASIS 9) - Patient						
(A9: Overall, how is the acne on your face right now?)						
Clear / Almost clear	%	p	%	p	%	p
Moderate / Severe	%	p	%	p	%	p
Mild	%		%		%	
Acne Severity (ASIS 9) - Caregiver						
(Q1: Overall, how is the acne on your child's face right now?)						
Clear / Almost clear	%	p	%	p	%	p
Moderate / Severe	%	p	%	p	%	p
Mild	%		%		%	
How Face Looks (ASIS 10)						
(A10: Over the past 7 days, rate how your face looked because of your acne.)						
Excellent/Very good	%	p	%	p	%	p
Fair / Bad	%	p	%	p	%	p
Good	%		%		%	

Note: Data from Patient DCF; X patients had missing data;

Table 7.1.14. Patient Acne Severity and How Face Looks (with LOCF imputation)

Domain	Baseline (N=xx)	Week 4 (N=xx)	Week 8 (N=xx)	Week 12 (N=xx)
Acne Severity (ASIS 9)-Patient  A9: (Overall, how is the acne on your face right now?)	N  Mean (SD) Median Min,Max	N  Mean (SD) Median Min,Max	N  Mean (SD) Median Min,Max	N  Mean (SD) Median Min,Max
Clear (0)	n (%)	n (%)	n (%)	n (%)
Almost clear (1)	n (%)	n (%)	n (%)	n (%)
Mild (2)	n (%)	n (%)	n (%)	n (%)
Moderate (3)	n (%)	n (%)	n (%)	n (%)
Severe (4)	n (%)	n (%)	n (%)	n (%)
Clear/almost clear	n (%)	n (%)	n (%)	n (%)
Moderate / Severe	n (%)	n (%)	n (%)	n (%)
Mild	n (%)	n (%)	n (%)	n (%)
Acne Severity (ASIS 9) - Caregiver  Q1: Overall, how is your child's acne on his/her face right now? (Week 4 & 8)	N  Mean (SD) Median Min,Max	N  Mean (SD) Median Min,Max	N  Mean (SD) Median Min,Max	N  Mean (SD) Median Min,Max
Clear (0)	n (%)	n (%)	n (%)	n (%)
Almost clear (1)	n (%)	n (%)	n (%)	n (%)
Mild (2)	n (%)	n (%)	n (%)	n (%)
Moderate (3)	n (%)	n (%)	n (%)	n (%)
Severe (4)	n (%)	n (%)	n (%)	n (%)
Clear/almost clear	n (%)	n (%)	n (%)	n (%)
Moderate / Severe	n (%)	n (%)	n (%)	n (%)
Mild	n (%)	n (%)	n (%)	n (%)
Face Look (ASIS 10)	N  Mean (SD) Median	N  Mean (SD) Median	N  Mean (SD) Median	N  Mean (SD) Median

A10: (Over the past 7 days, rate how your face looked because of your acne.)	Min,Max	Min,Max	Min,Max	Min,Max
Excellent (0)	n (%)	n (%)	n (%)	n (%)
Very good (1)	n (%)	n (%)	n (%)	n (%)
Good (2)	n (%)	n (%)	n (%)	n (%)
Fair (3)	n (%)	n (%)	n (%)	n (%)
Bad (4)	n (%)	n (%)	n (%)	n (%)
Excellent / very good	n (%)	n (%)	n (%)	n (%)

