**Table 7.1.15. CFB in Patient Acne Severity and How Face Looks (with LOCF imputation)**

Domain	CFB in Proportion at Week 4	p- value	CFB in Proportion at Week 8	p- value	CFB in Proportion at Week 12	p- value			
	N=xx		N=xx		N=xx				
Acne Severity (ASIS 9) - Patient									
(A9: Overall, how is the acne on your face right now?)									
Clear / Almost clear	%	p	%	p	%	p			
Moderate / Severe	%	p	%	p	%	p			
Mild	%		%		%				
Acne Severity (ASIS 9) – Caregiver									
(Q1: Overall, how is the acne on your child's face right now?)									
Clear / Almost clear	%	p	%	p	%	p			
Moderate / Severe	%	p	%	p	%	p			
Mild	%		%		%				
How Face Looks (ASIS 10)									
(A10: Over the past 7 days, rate how your face looked because of your acne.)									
Excellent/Very good	%	p	%	p	%	p			
Fair / Bad	%	p	%	p	%	p			
Good	%		%		%				

Note: Data from Patient DCF.

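### The SAP drops the protocol's continuous change from baseline for ASIS items 9 and 10 without giving a reason, so no planned table gives the SD, a confidence interval or a paired test of patient-level change

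*SAP*

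**What the plan says.** Both items are scored 0 to 4 and are asked at baseline and Weeks 4, 8 and 12. The rest of the ASIS is asked only at baseline and Week 12 (Protocol 8.1, SAP 5.1).

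- **Protocol 12.6.4:** "CFB in select individual items of ASIS, most specifically, items # 9 & 10, will be conducted by treating these variables as continuous variables". This applies at Week 12 and, if data allow, at Weeks 4 and 8.
- **SAP 6.6.4:** the same change becomes "CFB in proportion of individuals reporting specific response for select individual items of ASIS, most specifically, items # 9 & 10". The variables are declared discrete and grouped into two-category bands, at Weeks 4, 8 and 12.
- **SAP 6.3.1 (banding):** "the top-two response categories (of a likert scale) for a given question at Baseline will be grouped together into a single group proportion", compared with the same grouping at follow-up. The step is repeated at the other end of the scale. For item 9 the bands are 0–1, 2 and 3–4.
- **SAP 6.3.1 (tests):** "CFB in proportion of patients reporting a particular response to an outcome measure at a particular timepoint (such as Week-12) will be assessed using a" chi-square test, with no mention of pairing. Continuous changes get a paired t-test.
- **SAP Tables 7.1.13 and 7.1.15:** a percentage change per band and p-values for the two outer bands, without and with LOCF. Nothing else.
- **SAP Tables 7.1.12 and 7.1.14:** N, mean (SD), median, range and all five categories for both items at each visit.

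**The concern.** The protocol's analysis works on each patient's own difference on the 0–4 scale. The SAP's works on the difference between two cohort proportions. Three things follow.

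1. A patient who goes from severe to moderate, from bad to fair, or from almost clear to clear adds nothing to either band's change.
2. Once the items are declared discrete, they lose the change summary and paired t-test that the SAP gives to continuous measures. The ASIS domain scores keep theirs (Table 7.1.10), but only at Week 12.
3. At Weeks 4 and 8 patients answer only these two ASIS items, so no continuous patient-reported change is left at those visits.

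In a descriptive study the description is the product. Change in PROs is a listed additional endpoint at Week 12, and the Week 4 and 8 results will be read as the time course of response.

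**Working it through.** The documents contain no power, efficiency or precision figure for these items, so there is none to reproduce. Four checks were made.

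**1. What the change tables cannot see.** Take N = 250 (illustrative) and let 75 patients go from 4 to 3 while nobody else moves.
- Mean change = −75/250 = −0.30.
- Change in moderate/severe = 0. Change in clear/almost clear = 0.

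**2. What can be recovered elsewhere.** In the LOCF table (7.1.14) the mean change can be read as a difference of visit means where the same patients contribute. In the unimputed table (7.1.12) N may differ by visit. Neither gives the SD of change, because that needs the within-patient correlation: SD² of change = SD₁² + SD₂² − 2ρ·SD₁·SD₂, and ρ is not reported. So neither a paired interval nor individual shifts can be recovered.

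**3. Information kept by one band relative to the mean change.** All inputs here are assumed. The model is a bivariate normal cut into five levels. It was run over 48 combinations: four baseline distributions with 50–90% of patients in categories 3–4, shifts of 0.3, 0.8, 1.3 and 1.8 latent SD, and correlations of 0.2, 0.4 and 0.6.

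Relative efficiency = (Δp² / V) / (mean change / SD of change)².
- Paired: V = discordant share − Δp².
- Unpaired chi-square: V = 2·p̄(1 − p̄).

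One case in full: baseline 0/2/13/55/30%, shift 0.8, correlation 0.4.
- Mean change −0.56, SD 0.89: (0.56/0.89)² = 0.396.
- Moderate/severe falls from 0.85 to 0.59, so Δp = 0.26 and p̄ = 0.72.
- Unpaired: 0.0676 / (2 × 0.72 × 0.28) = 0.168, and 0.168/0.396 = 0.42.
- Paired, with 31% leaving the band and 5% entering: V = 0.36 − 0.0676 = 0.292. Then 0.0676/0.292 = 0.231, and 0.231/0.396 = 0.58 (0.57 before rounding).

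| Information kept over the 48 cases | Paired | Unpaired chi-square |
|---|---|---|
| Clear/almost clear | 8–74% (median 27%) | 6–49% (median 21%) |
| Moderate/severe | 28–84% (median 55%) | 18–58% (median 38%) |
| Better of the two | 37–84% (median 58%) | 24–58% (median 38%) |

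The better band therefore loses 16–63% if paired and 42–76% with the unpaired test. It loses more than half in 25% and 87.5% of the cases respectively. Part of the unpaired loss comes from ignoring the pairing, not from banding. Of all patients who moved, 6–62% stayed inside a band; the share is highest with a small shift and a severe baseline.

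A closed-form check for cutting a normal variable at share q: information kept = φ(z_q)²/[q(1 − q)]. This gives 64% at q = 0.5, 49% at 0.2 and 34% at 0.1.

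**4. Power, simulated.** N = 250, assumed baseline 1/3/16/50/30%, correlation 0.4–0.6, two-sided 0.05.

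| Shift (latent SD) | Paired mean change | Clear/almost clear, McNemar | Moderate/severe, McNemar |
|---|---|---|---|
| 0.2 | 70–84% | 20–24% | 44–53% |
| 0.3 | 96–99% | 42–49% | 80–88% |
| 0.5 | about 100% | 88–94% | over 99% |

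With the chi-square test read as unpaired, the two bands have about 13–17% and 33–34% power at a shift of 0.2. At 0.5, clear/almost clear still has about 84–86%.

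**The case against.** The strongest reply is that little is lost and that the protocol half-invites the bands. Protocol 12.4 already names the clear/almost clear and the very good/excellent proportions as Week 12 summaries, and lets ASIS responses be categorical, continuous or both. Domain scores that contain both items keep a continuous Week 12 change with a paired t-test. No early-response endpoint is listed, and SAP 6.3.1 makes all testing exploratory. All of this stands, and it limits the weight of the point. It does not justify the removal. Protocol 12.4 and 12.6.4 specify separate analyses; the SAP keeps the first (SAP 6.4) and drops the second.

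The documents do not support four stronger readings that a reader might reach.

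- **That the SAP reports nothing but band proportions.** Tables 7.1.12 and 7.1.14 show a cohort shift from severe to moderate. The blindness is confined to the change tables.
- **That banding is what hides patients who worsen.** Mean change hides them too. With 250 patients, 200 improving and 50 worsening by one point gives (−200 + 50)/250 = −0.60. So does 150 improving and none worsening: −150/250 = −0.60. Neither document plans a count of patients who worsened.
- **That half or more of the information is always discarded.** For the better band analysed as paired, that is true in only a quarter of the cases examined. The calculation also scores each band alone, although both are reported.
- **That early improvement is mostly a move the bands miss.** The documents give no figure for this. Moderate to mild and mild to almost clear both cross a band edge. On the baseline assumed for the power runs, 50% + 16% = 66% of patients start where a one-step improvement counts.

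**Conclusion.** The departure from the protocol is plain from the two texts and needs no assumption: continuous change in Protocol 12.6.4, banded proportions in SAP 6.6.4, no reason given, and no planned output with the SD, interval or paired test of patient-level change in items 9 and 10. At Weeks 4 and 8 no continuous patient-reported change remains.

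The size of the loss does rest on assumptions. The documents give no baseline distribution for either item, no within-patient correlation and no expected shift. Entry at IGA 3 or 4 makes a severe patient-rated baseline likely, but that is an inference. Under the assumptions shown, the loss is substantial for small shifts from a severe baseline (about 16–63% for the better band if paired), and power is high by every method at 0.5 latent SD. The effect is on precision and description, not on any confirmatory conclusion. It is a modest fault, worth correcting because the correction is cheap.

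**What to change.** In SAP 6.6.4 and Tables 7.1.13 and 7.1.15:

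1. Restore the protocol's continuous change for items 9 and 10 at Weeks 4, 8 and 12: N, mean and SD of patient-level change, 95% CI, and the paired t-test that SAP 6.3.1 already assigns to continuous changes. The interval goes beyond what the protocol asks for. With an assumed SD of change of 0.9–1.1 and 200–300 patients, its half-width would run from 1.96 × 0.9/√300 = 0.10 to 1.96 × 1.1/√200 = 0.15 points.
2. Add n (%) improved by at least one category, unchanged and worsened. This too is new to both documents. It is needed because neither the bands nor the mean change shows worsening.
3. Keep the two-category bands as a display. If they are tested, use a paired test.
4. If the sponsor prefers the bands alone, record the departure from Protocol 12.6.4 and the reason.

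The cost is one extra block in two tables, from data already collected.
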